## Study Protocol and Statistical Analysis Plan

**Study Title:** Beyond Confounders: Addressing Source of Measurement Variability and Error in Shear Wave Elastography

**NCT number:** NCT03342560

**Document date:** 08/20/2019

**HYPOTHESIS:** We hypothesize that variation using ultrasound elastography (UE) for the estimation of stage of liver fibrosis in patients with diffuse liver disease exists due to different methods of measurements, and/or different systems.

**BACKGROUND:** Liver disease and cirrhosis are important causes of morbidity and mortality in the United States and are a major public health problem with 40,000 deaths and more than 1.4 billion dollars spent on medical services. Hepatic fibrosis is the final common pathway for many different liver insults and is known to be a dynamic process, which is reversible if diagnosed early and treated. If untreated, fibrosis eventually progresses to cirrhosis, which is irreversible. The diagnosis of fibrosis relies on liver biopsy (the gold standard) however, is an invasive procedure with risks and sampling errors. Indirect biomarkers of fibrogenesis can measure some of these components to determine categories of fibrosis, with a sensitivity and specificity of 47% and 90% respectively. It is shown in the literature that, fat content of liver is related with fibrosis development. Biopsy is accepted as the most accurate technique to assess liver fat and fibrosis amount. Fibrotic livers demonstrate increased stiffness, a property that can be measured using technology named Ultrasound Elastography or sonoelastography (SWE). SWE is performed by insonating the patient with a low energy, amplitude, and frequency shear wave created by a vibrating probe. The propagated wave travels faster with increasing fibrosis: the stiffer the tissue, the faster the shear wave propagates. A pulse-echo ultrasound acquisition allows measurement of the wave velocity and the results are presented as kilopascals (kPa). Prior reports have described sensitivity and specificity for liver fibrosis detection of 80% and 97% respectively for SWE. The benefits of SWE are that it is inexpensive, reproducible, painless, rapid (< 10 min), easy to perform, and can be used for diagnosis, prognosis and monitoring disease progression.

### SPECIFIC AIMS:

- Compare shear wave elastography (SWE) measurements from different ultrasound systems; using histopathology as reference standards.
- Assess intra-operator and inter-operator reliability by measuring variability in elastography values by two operators on a single system.
- Determine the effect of deviations from guidelines (less number of measurements and measurements during active breath)

The proposed investigation is a cross-sectional study using ultrasound elastography and fat quantification modalities. We enrolled 30 subjects 18 years old and older in whom diffuse liver disease was suspected, and who had undergone non-focal liver biopsy in the past 6 months or are scheduled to undergo biopsy within 3 months of enrollment, as part of their routine clinical care.

### Inclusion criteria:

- Adult patients (age 18 or older)
- Men or women

- Suspected diffuse liver disease and have had a liver biopsy within the last 6 months or are scheduled for a liver biopsy in the next 3 months.
- Consent to participate in the study

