**Exclusion criteria:**

- Pregnancy
- Acute illness/cognitive impairment resulting in inability to cooperate with ultrasound
- Patients that do not consent to ultrasound examination.

All subjects came for 2 study visits within 60 days of each other. In addition, subjects needed to fast for at least 4 hours prior to study visits. Sonoelastography was performed using four FDA-approved ultrasound units. 2 sonographers performed;

- Median Elastography (10 measurements) on regular and variable map at a depth(in the area between 2cm from capsule and 6.5cm from skin)
- Median SWE value with active/free breath(10measurements)
- Median SWE value with less number of acquisitions(3measurements)

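### Should the 6-month and 3-month biopsy limits be applied to each scan, and not only at enrolment, when elastography is compared with histology?

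*Combined protocol and SAP*

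**What the plan says.** Aim 1 in the Specific Aims section is to "Compare shear wave elastography (SWE) measurements from different ultrasound systems; using histopathology as reference standards". Biopsy timing appears in two places. The Inclusion criteria require that patients "have had a liver biopsy within the last 6 months or are scheduled for a liver biopsy in the next 3 months". The Specific Aims section describes the enrolled subjects as those "who had undergone non-focal liver biopsy in the past 6 months or are scheduled to undergo biopsy within 3 months of enrollment", which ties the 3-month limit to enrolment outright and the 6-month limit by implication.

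The visit schedule, printed after the Exclusion criteria, states: "All subjects came for 2 study visits within 60 days of each other". It continues: "Sonoelastography was performed using four FDA-approved ultrasound units". It does not say which system was used at which visit, or how soon after enrolment visit 1 took place.

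The Statistical Analysis Plan section names one analysis, an intraclass correlation for agreement within operators. It describes no comparison with histology, so it sets no biopsy-to-scan window and names no visit for Aim 1.

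**The concern.** A reference standard should describe the liver at the time it is scanned. The Background says that fibrosis "is known to be a dynamic process, which is reversible if diagnosed early and treated", and that it progresses if untreated. The study calls itself cross-sectional: "The proposed investigation is a cross-sectional study using ultrasound elastography and fat quantification modalities". Yet the only control on timing is an eligibility check, and the visit schedule lets the second scan drift beyond it. None of the exclusions (pregnancy, "Acute illness/cognitive impairment resulting in inability to cooperate with ultrasound", and lack of consent) deals with treatment begun between biopsy and scan.

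If a liver changed in that interval, a correct elastography reading would be counted as a disagreement with histology. In a study meant to separate sources of measurement error, elapsed time would then be one more source. Because the visit is not named, its choice could also decide whether a given scan lies inside 6 months, or before or after the biopsy. Only Aim 1 is exposed. Aims 2 and 3 and the intraclass correlation do not need the biopsy.

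**Working it through.** The documents state no biopsy-to-scan interval, so there is no figure of theirs to reproduce. The inputs are 6 months (about 182 days; 180 to 184 depending on the calendar), 3 months (about 91 days), at most 60 days between visits, and 30 subjects. The gap g from enrolment to visit 1 is not given and is varied.

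1. **Longest interval, biopsy first.** Biopsy to visit 2 is at most 182 + g + 60 days.
   - With g = 0 this is 242 days (240 to 244 over the calendar range), which is 60 days, or 60/182 = 33%, beyond 6 months.
   - With g assumed to be 14, 30, 60 or 90 days, the excess is 74, 90, 120 or 150 days, and visit 1 itself is over by g days. So 60 days is not a ceiling.

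2. **Share of scans involved.** Assume g = 0 and biopsy dates spread evenly over the 182 days before enrolment. With visits d days apart, the share of visit 2 scans beyond 182 days is d/182: 14/182 = 7.7%, 30/182 = 16.5%, 60/182 = 33.0%. The split between past and scheduled biopsies is unknown. If 15 subjects were biopsied first, that is 1.2, 2.5 or 4.9 of them; if all 30 were, 2.3, 4.9 or 9.9.

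3. **Scheduled biopsies.** With g = 0 and the biopsy done within 91 days, visit 1 is at most 91 days from biopsy and visit 2 at most 60. Neither exceeds 3 months. The biopsy may fall between the visits (d/91 = 15.4%, 33.0% or 65.9% for d = 14, 30 or 60, if biopsy dates are spread evenly), but both scans are then within 60 days of it. Those are close pairings, not a measure of harm. The real looseness in this branch is that the biopsy need only be scheduled: it could slip, or not be done.

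4. **What a 182-day cut-off would achieve.** Under step 2 with d = 60, visit 2 intervals run evenly from 60 to 242 days, with mean (60 + 242)/2 = 151. Cutting at 182 leaves 60 to 182, with mean (60 + 182)/2 = 121. The mean lag falls by 30 days, or 30/151 = 20%, and 33% of the biopsy-first visit 2 scans are lost.

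5. **Possible effect on accuracy.** Aim 1 names no accuracy measure, so this is illustration only. Take the Background's 80% sensitivity and 97% specificity, and assume 15 biopsy-positive subjects.
   - Each subject who had become negative by the scan lowers apparent sensitivity by (0.80 − 0.03)/15 = 5.1 points.
   - For a system with the same sensitivity and an assumed 80% specificity, the loss is (0.80 − 0.20)/15 = 4.0 points.
   - With three such subjects the second system gains 3 × (0.20 − 0.03)/15 = 3.4 points, or 0.034 × 15 = 0.5 of a subject. For scale, the standard error of one sensitivity of 80% in 15 subjects is √(0.80 × 0.20/15) = 10.3 points.
   - This loss follows from any change between biopsy and scan, including one well inside 6 months. It is not tied to the extra 60 days.

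**The case for a change.** The best case for acting is that it would cost little. The sponsor chose 6 and 3 months as tolerable distances from biopsy, so applying them where the comparison is made only carries that judgement through. The lag need not cancel between systems: a less specific system still calls some regressed livers positive and is credited for it. Leaving the visit open lets it be chosen after results are seen. A short rule and one table would deal with this, with eligibility and visits untouched.

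Part of this stands. No window is set, no visit is named, and differential bias is possible in principle. A report of Aim 1 that omitted the interval would be poorer for it.

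The rest is weaker:

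- The 6 and 3 months decide who may enter. Nothing in the documents makes them a standard for valid scans, so using them as an analysis cut-off is a fresh choice.
- If one system was used only at visit 2, excluding late scans removes subjects from that system alone, and the systems are then compared on different people.
- Even with every system used at visit 1, completeness is not assured, because a postponed or cancelled biopsy would put a scheduled-branch subject outside the limit or leave no histology.
- The freedom to choose a visit is one part of a wider gap, namely that the plan describes no histology analysis at all. Fixing the visit alone would not close it.

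**Conclusion.** No change follows. The observation is accurate: the limits apply at enrolment, and a visit 2 scan can fall 60 days or more beyond 6 months after biopsy. But no rule is broken, no subject is shown to have changed stage, and the documents neither include nor exclude visit 2 scans in Aim 1. Without biopsy dates, visit dates or a rate of change, the bias cannot be estimated. The only figures for scope, 8% to 33% of biopsy-first visit 2 scans, assume visit 1 at enrolment, evenly spread biopsy dates and visits 14 to 60 days apart.

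The suggestion has two parts. Stating the visit used, taking all systems from the same visit where the data allow, and giving the biopsy-to-scan interval are details a competent analyst would supply in any report of Aim 1, if the dates were recorded. Making the 6-month and 3-month limits the rule for the main comparison is a debatable trade-off: on the assumptions above it shortens the mean visit 2 lag by about 20%, can cost up to a third of the biopsy-first scans, and puts the same-subject comparison of systems at risk. Enrolment and visits are reported as complete, so the design itself can no longer be tightened.

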**Exclusion criteria:**

- Pregnancy
- Acute illness/cognitive impairment resulting in inability to cooperate with ultrasound
- Patients that do not consent to ultrasound examination.

All subjects came for 2 study visits within 60 days of each other. In addition, subjects needed to fast for at least 4 hours prior to study visits. Sonoelastography was performed using four FDA-approved ultrasound units. 2 sonographers performed;

- Median Elastography (10 measurements) on regular and variable map at a depth(in the area between 2cm from capsule and 6.5cm from skin)
- Median SWE value with active/free breath(10measurements)
- Median SWE value with less number of acquisitions(3measurements)

**STATISTICAL ANALYSIS PLAN:**

Statistical analysis software to use: SPSS (Release 24, IBM, NY, USA) software.

Intra-operator agreement between each operators' median measurement was calculated using ICC (Intraclass correlation coefficient). 95% confidence intervals were computed for parameter estimates. All p-values were two sided. p values less than 0.05 were considered statistically significant.

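### Aim 2 asks for intra-operator and inter-operator reliability, but the SAP gives one ICC whose label and wording point to different comparisons, so one of the two objectives has no analysis as written

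*Combined protocol and SAP*

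**What the plan says.** The second item under Specific Aims reads "Assess intra-operator and inter-operator reliability by measuring variability in elastography values by two operators on a single system". That is two objectives, restricted to one system.

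The Statistical Analysis Plan section answers with one sentence: "Intra-operator agreement between each operators' median measurement was calculated using ICC (Intraclass correlation coefficient". The rest of that section covers only the software, 95% confidence intervals, two-sided p-values and the 0.05 threshold. Inter-operator agreement is not named anywhere in it.

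The study procedures, printed after the exclusion criteria, give the raw material from which pairs could be formed. On visits: "All subjects came for 2 study visits within 60 days of each other". On equipment: "Sonoelastography was performed using four FDA-approved ultrasound units". On operators: "2 sonographers performed", followed by a list of medians taken under different acquisition conditions. Nothing there is linked to an ICC.

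**The concern.** The two reliabilities answer different questions. Inter-operator reliability asks whether two sonographers are interchangeable on the same patient. Intra-operator reliability asks whether one sonographer can repeat his or her own value. An ICC for one is not an estimate of the other.

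The SAP sentence is labelled as the second but is worded much like the first. An analyst following it would have to guess, and either guess leaves half of Aim 2 without a planned analysis. If the guess is operator 1 against operator 2, the result would also carry the wrong name.

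The study's title and hypothesis concern where measurement variability comes from. An ICC whose source of variability is mislabelled or unknown therefore fails on the question that the study set out to answer.

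**Working it through.** The plan gives no ICC, target ICC or variance component, so there is no figure to reproduce. The check compares the aim with the analysis.

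**Step 1: what Aim 2 needs.** (i) Inter-operator: values from operator 1 and operator 2 on the same subject. (ii) Intra-operator: repeated values from the same operator on the same subject. Both are on one system.

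**Step 2: what the SAP supplies.** One ICC. Its label is intra-operator; the quantity compared is the operators' medians, joined by a word that normally introduces two different things being compared.

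**Step 3: test each reading.**

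| Reading of the SAP sentence | Inter-operator | Intra-operator | Label |
|---|---|---|---|
| Label governs: each operator against own repeats | no analysis | analysed | correct |
| Wording governs: operator 1 against operator 2 | analysed | no analysis | wrong |

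One of the two objectives is uncovered in each row.

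**Step 4: look for a repair elsewhere.** The procedures text mentions 2 visits and 2 sonographers. It does not say that both sonographers scanned a given subject at the same visit, or that one sonographer scanned a given subject twice on the same system. It neither defines the pairs nor confirms that they exist.

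**Step 5: can one ICC stand in for the other?** This is an illustration only; every variance is an assumption. Let S be the variance between subjects, O the variance between operators and E the residual error.

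- Inter-operator, absolute agreement: S / (S + O + E)
- Intra-operator, computed within one operator so that a constant operator shift cancels: S / (S + E)

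With S = 1.0 and E = 0.1:

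| Assumed O | Inter-operator | Intra-operator |
|---|---|---|
| 0 | 1/1.1 = 0.909 | 1/1.1 = 0.909 |
| 0.1 | 1/1.2 = 0.833 | 1/1.1 = 0.909 |
| 0.3 | 1/1.4 = 0.714 | 1/1.1 = 0.909 |

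The two coincide only when the operators do not differ, which is what Aim 2 is meant to find out.

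The ordering in the table is not guaranteed in this study. Suppose the intra-operator repeats are the two visits, and V is the variance of a subject's own change between visits. The intra-operator ICC becomes S / (S + V + E), while a same-visit inter-operator ICC becomes (S + V) / (S + V + O + E). With O = 0 and V above 0, the intra-operator value is then the lower one. So neither the size nor the direction of a mislabelling error can be read from the documents.

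**The case against.** The strongest reply is that the sentence is compressed and was meant to cover agreement both within and between operators, and that 2 sonographers and 2 visits may have produced data for both. This is possible. But the text does not say it, and the SAP never names inter-operator agreement. Even if the intention is granted, the pairs and the ICC form are unstated for both analyses, so the same correction is needed.

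A second reply is that the study is described in the past tense, so rewording a plan changes little. What stands of this is that rewording cannot create pairs that were not collected. It still matters for how each reported ICC is labelled and which claims are kept.

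Three stronger conclusions are tempting, and the documents do not support them.

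- A reader might infer that neither Aim 2 objective is analysed, because the ICC could pair one operator's medians across acquisition conditions such as "Median SWE value with active/free breath(10measurements". That is strained. The SAP sentence uses a reliability term and mentions no map, breathing state or number of acquisitions; the effect of such deviations is a separate aim.
- A reader might try to size the problem by counting the possible pairs of medians per subject. Any such count rests on an assumed layout and bounds nothing: repeat sets within a visit, or separate medians per map for every condition, would raise it.
- A reader might infer that the needed pairs were never collected, or that a wrong ICC was in fact reported. The documents show neither.

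**Conclusion.** The concern holds. Aim 2 has two objectives and the SAP specifies one ICC, with a label that conflicts with its wording. Under each of the two natural readings, one objective of two has no analysis as written, and under one of them a between-operator ICC would be reported as intra-operator.

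That is the full size that the documents support. No numerical effect on an ICC can be stated, and the values in the illustration are not estimates for this trial. The conclusion assumes that the SAP sentence is complete as printed; nothing marks it as redacted or damaged. It does not depend on which of the four units is the Aim 2 system or which map was used. Those are separate gaps in specification.

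**What to change.** Replace the sentence with two named analyses on the single Aim 2 system, using the same type of median in both and giving a 95% confidence interval for each ICC:

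- **Inter-operator:** operator 1 against operator 2 on the same subject, two-way absolute-agreement single-measure ICC. Use the same visit where both operators scanned at it; otherwise state that operator and visit are confounded.
- **Intra-operator:** each operator's own repeats of that median, absolute-agreement single-measure ICC, reported per operator with its model stated. If the repeats are the two visits, state that the ICC includes change between visits up to 60 days apart.

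Label any ICC already computed by the pairing actually used. Because the text reports work already done, present added ICCs as added later and not as prespecified. Withdraw whichever reliability claim has no matching pairs in the data.

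The cost is a few lines of SAP text and one or two more ICCs if the pairs exist. If they do not, Aim 2 becomes narrower.

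### The one reliability statistic named, an ICC, gives neither the size of the measurement error nor a systematic shift, and one half of Aim 2 has no clearly named statistic

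*Combined protocol and SAP*

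**What the plan says.** The study title sets the subject as "Addressing Source of Measurement Variability and Error in Shear Wave Elastography". The second item under Specific Aims is to "Assess intra-operator and inter-operator reliability by measuring variability in elastography values by two operators on a single system". The Background says of the elastography reading that "the results are presented as kilopascals (kPa").

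The Statistical Analysis Plan is a software statement followed by four sentences. One names a reliability statistic: "Intra-operator agreement between each operators' median measurement was calculated using ICC (Intraclass correlation coefficient"). The other three are general: "95% confidence intervals were computed for parameter estimates", "All p-values were two sided" and "p values less than 0.05 were considered statistically significant". They do not say which parameters or tests they cover.

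Nowhere do the documents name a mean difference, limits of agreement, within-subject SD, coefficient of variation or repeatability coefficient. The ICC's model, its type (consistency or absolute agreement) and its unit (single or average) are not stated. On repeats, the text after the Exclusion criteria says "All subjects came for 2 study visits within 60 days of each other" and refers to two sonographers. It does not say whether the intra-operator repeats are the two visits or repeats within one visit.

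**The concern.** The aim has two parts, and the method it gives for both is to measure variability. The plan answers with one index, whose description points two ways: the label is intra-operator, but the phrase about agreement between each operator's median could describe a comparison of the two operators. One part of the aim is therefore left without a clearly named statistic.

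The second issue is what an ICC can show. It is the share of total variance that comes from differences between patients. A cohort with widely spread stiffness can give a high ICC despite large errors, and a narrow cohort a modest ICC despite small ones. A reader of a study on measurement error will want to know how many kPa, or what percentage, two readings of the same liver may differ by, and whether one operator or occasion reads higher. An ICC, with or without its confidence interval, does not tell them.

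**Working it through.** The plan gives no SD, target ICC or margin, so there is no figure of its own to reproduce. From the documents come 30 subjects, two operators, two visits and the kPa scale. All spreads and shifts below are assumptions for illustration.

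**1. The same ICC fits very different errors.** On the log scale, let b be the between-subject SD and e the within-subject error SD.

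- ICC = b²/(b² + e²). Setting this to 0.90 gives e = b/3.
- Within-subject CV = √(exp(e²) − 1).
- 95% ratio limits of agreement = exp(±1.96 × √2 × e).

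| b | e | CV | Ratio limits |
|---|---|---|---|
| 0.2 | 0.067 | 7% | 0.83 to 1.20 |
| 0.3 | 0.100 | 10% | 0.76 to 1.32 |
| 0.5 | 0.167 | 17% | 0.63 to 1.59 |
| 0.7 | 0.233 | 24% | 0.52 to 1.91 |

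The kPa scale shows the same. For between-subject SDs of 2, 4, 6 and 8 kPa, an ICC of 0.90 fits repeatability coefficients (1.96 × √2 × within-subject SD) of 1.85, 3.70, 5.54 and 7.39 kPa.

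**2. The same error gives very different ICCs.** With e fixed at 0.15, the ratio limits are always 0.66 to 1.52. The ICC is 0.0400/0.0625 = 0.64 at b = 0.2, 0.0900/0.1125 = 0.80 at 0.3, 0.2500/0.2725 = 0.92 at 0.5 and 0.4900/0.5125 = 0.96 at 0.7.

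**3. A systematic shift.** For two ratings with a constant shift d, between-subject SD sb and error SD sw:

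- Consistency ICC = sb²/(sb² + sw²), which does not contain d.
- Absolute-agreement ICC = sb²/(sb² + sw² + d²/2).

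With sb = 4 and sw = 1 kPa, the consistency form is 16/17 = 0.941 at any shift. The absolute-agreement form is 0.941, 0.914, 0.842 and 0.744 at shifts of 0, 1, 2 and 3 kPa. It does fall, but it does not identify the cause: 16/(16 + 1 + 2) = 0.842 arises from a 2 kPa shift with error variance 1, and equally from no shift with error variance 3. Because d enters squared, the direction is lost as well.

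**4. The confidence interval does not fill the gap.** For a one-way ICC with 30 subjects and two ratings, an observed 0.90 has an F-based 95% CI of 0.80 to 0.95. That is sampling uncertainty in a relative index, not a range for the difference between two readings.

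**5. Precision of the added measures.** This assumes that all 30 subjects give a complete pair.

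- Mean difference: t(29)/√30 = 0.37 SD of the differences either side.
- Each limit of agreement: t(29) × √(1/30 + 1.96²/58) = 0.645 SD of the differences either side.
- Within-subject SD (29 df): 95% CI from 0.80 to 1.34 times the estimate.

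**The case against.** An ICC is a standard reliability index and the aim uses the word reliability, so the choice is not wrong. That stands: the ICC should stay, and the request is to add to it.

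A reader might infer that the study has no inter-operator analysis at all. The documents do not support that. The intra-operator label may be a slip, and the ICC may compare the two operators. What can be said is that the sentence does not settle which half of the aim it serves.

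A reader might also infer that the ICC would conceal a shift entirely. That is true only of the consistency form. The form is not stated, and the word agreement leans towards the absolute form, which falls as a shift grows. What remains is that neither form reports the size or direction of the shift.

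The spreads and shifts are all assumed, and a single cohort has only one between-subject spread. The contrast between the ends of the table is therefore not a forecast for this study. That also stands.

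Finally, the document is short and written in the past tense. Its general sentences on intervals and p-values imply estimates and tests that it does not list, so omission here does not show that other analyses were not done. Taken alone, the unstated ICC form and visit structure are missing detail. What goes beyond that is the absence of any named output that measures error on the reading's own scale.

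**Conclusion.** The point holds as a worthwhile, inexpensive improvement, not as a finding that the ICC is invalid. Followed as written, the plan would yield a relative index for one comparison, whose identity is unclear. It would yield no error size in kPa or percent, no size or direction of any shift, and no clearly named statistic for the other half of Aim 2.

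This rests on the text and the definition of the ICC, and does not need the assumed SDs. Those only illustrate the scale: at an ICC of 0.90, the upper limit for a second reading against a first of 10 kPa is 12.0 kPa at log SD 0.2 and 19.1 kPa at log SD 0.7. The true spread, and whether any shift exists, are unknown, so the practical effect here cannot be stated. The past tense also does not show that the ICC form was chosen after the data were seen.

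**What to change.** For the intra-operator comparison (each operator separately) and for the inter-operator comparison, report alongside the ICC:

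- the mean difference with 95% CI;
- the 95% limits of agreement with CIs;
- the within-subject SD, or the CV with log-scale analysis if error grows with the mean.

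Say which comparison each ICC covers, and state its model, type and unit. Say whether the intra-operator repeats are within one visit or are the two visits up to 60 days apart. If they are the visits, note that the within-subject SD includes real change in the liver and is not operator error alone.

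Label these analyses as added after data collection where that is so. Label the ICC form that way only if it was in fact chosen then.

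The cost is some wording and a few extra outputs from data already collected. Precision with 30 subjects is moderate, as shown in the working, so the limits need their confidence intervals beside them.
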